As for the rationale for the proposed expansion cohort, this is based on the promising finding of the dose-escalation phase of the study. After enrollment of the 18 patients for the dose-escalation phase, 8 patients were treated with DSF of 250 mg/day (dose level 2) and 10 patients with 375 mg/day (dose level 3). Three dose-limiting toxicities (DLTs) were observed: 1 with 250 mg/day (grade 2 urinary incontinence and ataxia), and 2 with 375 mg/day (both grade 3 elevated liver enzymes). The TITE-CRM model estimated the DLT probability of DSF to be 10% (95% CI: 3-29%) at 250 mg/day, and 21% (95% CI: 7-42%) at 375 mg/day. Thus, we have declared that the MTD of DSF in combination with RT/TMZ/Cu for GBM is 375 mg/day, and the recommended phase II dose is 250 mg/day. Furthermore, tumor mutations were evaluated with next-generation sequencing for all patients to explore possible biomarkers for response. Notably, GBM patients with *IDH* (n = 6), *BRAF* (n = 2), and *NF1* (n = 1) mutations exhibited much better PFS and OS than those without these mutations (n = 9): 1-year PFS of 100% vs 22%, respectively, p = 0.001; 1-year OS of 100% vs 42%, respectively, p = 0.006. Given that the historical PFS and OS of newly diagnosed GBM patients treated with RT and TMZ is approximately 27% and 60% at one year [4], respectively, the preliminary data of this molecular subset of GBM are thought-provoking and raise the possibility that these mutations make GBM tumors more sensitive to DSF/Cu in combination with chemoradiotherapy. Interestingly, all three mutations, which affect approximately 15-20% of GBM tumors, make tumor cells more dependent on glutamate for cellular metabolism [68-70]. As DSF metabolite can affect glutamate uptake, this may be the biological mechanism for the improved outcomes for GBM with these mutations. Thus, we have proposed to add an expansion cohort to this phase I/II study to treat additional GBM patients with *IDH*, *BRAF*, or *NF1* mutations to increase the statistical power of our preliminary finding.

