
#### **14.3.5 Sample Size for the Dose-expansion Phase**

To further explore the effect of the addition of DSF/Cu to standard chemoradiotherapy for the subset of GBM with *IDH/BRAF/NF1* mutations, we propose to add an expansion cohort to further confirm that the addition of DSF/Cu to chemoradiotherapy may be a promising strategy to treat GBM with these mutations. Given historical data for a cohort of GBM is not readily available, some assumptions are used to derive a historical control benchmark. GBM with *BRAF* or *NF1* mutations are not known to have different prognosis than typical *IDH*-wildtype GBM [81,82], with historical OS of approximately 30% at 2 years and 10% at 5 years [3,83,84]. Both *BRAF* and *NF1* mutations affect the RAS/MAPK pathway and can also occur in the same patient, thus we will combine both mutations into one molecular cohort. However, *IDH*-mutant GBM is known to have better OS than *IDH*-wildtype GBM, with 2 year OS of approximately 50% and 5 year OS of approximately 20% [85], so we will define the second molecular cohort by the presence of *IDH* mutation. Therefore, a cohort with equal proportion of *IDH*-mutant GBM and *BRAF/NF1*-mutant GBM should theoretically have 2 year OS of 40% and 5-year OS of 15%. Based on such assumptions, a sample size of 24 patients (including 12 with *IDH* mutations and 12 with *BRAF/NF1* mutations) would provide 80% power with one-sided alpha of 0.10 to detect an improvement of 2-year OS from historical 40% to 60% (or a hazard ratio of 0.55). Since we have already enrolled 9 patients with these mutations (6 with *IDH* mutation, 2 with *BRAF* mutation, and 1 with *NF1* mutation), only additional 15 patients will be needed: 6 with *IDH* mutation, 9 patients with *BRAF* and/or *NF1* mutations. For the dose-expansion phase, patients are considered evaluable if a patient has received at least 4 weeks of DSF with RT, at either the MTD (375mg/day) or the RP2D (250mg/day). Inevaluable patients will be replaced.

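### The nine patients whose survival suggested the mutation hypothesis are counted in the 24-patient primary OS comparison, so the stated one-sided alpha of 0.10 and 80% power do not describe it

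*Combined protocol and SAP*

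**What the plan says.** Section 1.3 reports that tumour sequencing of the 18 escalation patients was used to look for response biomarkers. Nine carriers of IDH (6), BRAF (2) or NF1 (1) mutations were compared with the nine non-carriers: "1-year PFS of 100% vs 22%, respectively, p = 0.001; 1-year OS of 100% vs 42%, respectively, p = 0.006". For context it adds that the "historical PFS and OS of newly diagnosed GBM patients treated with RT and TMZ is approximately 27% and 60% at one year". The expansion cohort is then proposed "to increase the statistical power of our preliminary finding".

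Section 14.3.5 gives the aim: "we propose to add an expansion cohort to further confirm that the addition of DSF/Cu to chemoradiotherapy may be a promising strategy". It sets a 2-year OS benchmark of 50% for IDH-mutant tumours. BRAF and NF1 "mutations are not known to have different prognosis than typical" IDH-wildtype disease, "with historical OS of approximately 30% at 2 years and 10% at 5 years". An equal mix gives 40%. Twenty-four patients, 12 per group, "would provide 80% power with one-sided alpha of 0.10 to detect an improvement of 2-year OS from historical 40% to 60" per cent, with a hazard ratio given as 0.55. The section continues: "Since we have already enrolled 9 patients with these mutations", only 15 more are needed, 6 with IDH and 9 with BRAF and/or NF1 mutations. The evaluability rule accepts both dose levels used in the escalation phase, so pooling is intended.

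OS of this cohort is the primary endpoint of the expansion phase (Sections 2.0 and 14.1). Sections 14.1 to 14.4 name no test for it, describe no adjustment for the nine, and plan no separate analysis of the 15.

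**The concern.** An alpha of 0.10 is the chance of a false positive in patients whose outcomes did not help to choose the hypothesis. Here 9 of 24 patients (37.5%) were singled out because they had done well. If disulfiram/copper had no effect, a group picked for surviving and staying progression-free to 1 year would still beat a 2-year benchmark meant for unselected patients. The pooled OS is therefore biased upward, and the same survival is used once to raise the hypothesis and again to support it.

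Readers will judge the primary result by the stated alpha and power. Neither applies once nine of the outcomes are partly known, and the error favours a positive conclusion.

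**Working it through.** **Inputs.** From Section 14.3.5: n = 24 (12 IDH, 12 BRAF/NF1); one-sided alpha 0.10; 2-year OS 40% versus 60%; group benchmarks 50% and 30%; 9 existing patients (6 and 3) and 15 new (6 and 9). From Section 1.3: 1-year PFS and OS of 100% in the nine. Their follow-up at the data cut is not given, so it is varied below.

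**1. The plan's 80%.** With log-log transformed 2-year OS and null variance:
- HR = ln 0.6 / ln 0.4 = 0.557, so ln(1/HR) = 0.584.
- SE0² = (1 − S0) / (n·S0·(ln S0)²) = 0.60 / (24 × 0.40 × 0.840) = 0.0744, so SE0 = 0.273.
- Power = Φ(0.584/0.273 − 1.2816) = Φ(0.860) = 0.805.

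A one-sample log-rank with 2 years' follow-up and HR 0.55 gives 0.786. Both describe 24 patients with unknown outcomes.

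**2. The implied rule.** The log-log statistic is 1.02 at 12/24 alive and 1.47 at 13/24, against 1.2816, so it rejects at 13 or more. The smallest count that keeps exact size below 0.10 is 14, so both are shown.

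**3. Size without selection.** Twelve patients at 0.50 and twelve at 0.30 (exact convolution) give 0.109 at ≥13 and 0.050 at ≥14.

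**4. Size given what is known of the nine.** Under the null, a patient alive at time e survives to 2 years with probability S(2)/S(e). Assumed 1-year null OS is 65–80% for IDH (no source in the documents) and 55–60% for BRAF/NF1. The 60% is the overall glioblastoma figure in Section 1.3, applied to BRAF/NF1 because Section 14.3.5 says no prognostic difference is known.
- Conditional 2-year OS: IDH 0.50/0.80 = 0.625 to 0.50/0.65 = 0.769; BRAF/NF1 0.30/0.60 = 0.50 to 0.30/0.55 = 0.545.
- Expected 2-year survivors among the nine: unselected 6 × 0.50 + 3 × 0.30 = 3.9; given alive at 1 year, 5.3 to 6.3.

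The progression-free rows use a model with exponential progression followed by exponential death, fitted to 1-year PFS of 27% (BRAF/NF1) and 27–50% (IDH) and to the 2-year benchmarks. The log-rank column uses nominal alpha 0.10, censoring at 2 years and 200,000 simulations per cell; its alive rows assume constant hazard.

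| Known status of the nine | ≥13/24 | ≥14/24 | Log-rank, all 24 |
|---|---|---|---|
| None (unselected) | 0.109 | 0.050 | 0.09 |
| Alive at 6 months, progression-then-death model | 0.14 | 0.07 | not run |
| Alive at 6 months, constant hazard | 0.20 | 0.10 | 0.19–0.22 |
| Progression-free at 6 months | 0.24–0.25 | 0.13 | 0.23–0.27 |
| Alive at 1 year | 0.25–0.40 | 0.14–0.25 | 0.35–0.39 |
| Progression-free at 1 year | 0.48–0.49 | 0.31–0.32 | 0.46–0.51 |

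Pooled power at ≥13/24 moves too, from 0.78 unselected to 0.89–0.94 given alive at 1 year.

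**5. The 15 new patients alone.**
- Benchmark: (6 × 0.50 + 9 × 0.30)/15 = 0.38.
- One-sample log-rank at 2 years: size 0.08–0.11 with a correct null curve, power 0.60–0.66 at HR 0.557.
- Exact count: ≥8/15 has size 0.163; ≥9/15 has size 0.066 and power 0.54.

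**The case against.** The pooling is disclosed, the cohort is a small single-arm extension, and the sentence that speaks of confirming also speaks of exploring. That makes a pooled description acceptable. It does not make a stated alpha and power true.

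The plan names no test, so the 13-of-24 rule is inferred. With ≥14/24 and only 6 months' follow-up, the illustrative size is 0.07 to 0.10, no higher than the stated figure. The upper rows need all nine observed for a full year, whereas 100% may be a Kaplan-Meier estimate with censoring. The progression-then-death model implies 5-year OS of 2% and 8–9%, below the plan's 10% and 20%. It is also assumed that all nine meet the 4-week evaluability rule. These points stand as limits on the size of the inflation, not on its direction: every row exceeds the unselected size of the same rule. None adds the selection involved in grouping three genes after seeing the data.

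The remedy can be called more than a rewording, since it names a test and a censoring time and the stated power drops well below 80%. That is fair as a description of the cost. But the plan has no test to displace, and the exact-count version needs only its own 2-year rates.

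**Conclusion.** The concern holds. The nine patients who generated the hypothesis are reused in its primary test, and the one-sided alpha of 0.10 and 80% power are given for the pooled 24 without adjustment. Those figures are correct only for 24 unselected patients.

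The true alpha cannot be computed. For a rule with unselected size 0.109, the illustrative false-positive chance runs from 0.14 to 0.49, depending on the nine patients' follow-up and the null curve. With all nine alive at 1 year it is 0.25–0.40. The direction of the bias does not depend on these assumptions; its size does.

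**What to change.** In Section 14.3.5, replace the 24-patient error statement with wording such as:

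> The primary test is a one-sided 0.10 one-sample log-rank test of OS from day 1 of RT in the 15 newly enrolled patients, censored at 2 years. Expected deaths are summed over the IDH null curve (6 patients, 50% at 2 years) and the BRAF/NF1 null curve (9 patients, 30% at 2 years). OS of all 24 patients is descriptive, because the 9 escalation patients generated the hypothesis.

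State the 1-year value of each null curve and its source, because the log-rank depends on the curve's shape before 2 years. If a constant-hazard null is used and is wrong, size is 0.08–0.13 over the 1-year values above and 0.13–0.16 under the progression-then-death model. If no source can be cited, use the exact count of at least 9 of 15 alive at 2 years.

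Restate the benchmark as 38%, with the size and power of the chosen test. A late-entry log-rank of all 24 can serve only as a sensitivity analysis. Its size is 0.09–0.11 if the nine are known only to be alive at entry, but 0.21–0.26 if they are also progression-free at 1 year.

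**Cost.** No added patients, visits or procedures. The chart review falls 2 years after coming off study (Section 5.13) or after the last disulfiram dose (Section 11.0). Both are later than 2 years from day 1 of RT, so 2-year status is available for everyone not lost to follow-up. Stated power falls from 80% to 0.60–0.66, or 0.54 with the count. Part of the fall comes from the test: 24 unselected patients give 0.75–0.78 with the same log-rank, and the formula in step 1 gives 0.67 for 15 patients against 38%. Keeping 80% with new patients only would take about 25–27 of them, 10–12 more than planned.

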### **5.9.3 Toxicity, Response, and DLT Evaluations**

All patients who receive at least one dose of DSF are evaluable for toxicity. However, patients have to receive the combination of DSF with RT+TMZ to be evaluable for DLT. Of note, DLT evaluation starts when patient starts DSF with RT and does not apply during the preoperative DSF administration. Patients who do not have at least one dose of DSF with RT+TMZ will not be evaluable for DLT and will be replaced.

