### **5.13 Duration of Follow-up**

Patients are evaluated for adverse events for 30 days after the last dose of DSF or until death, whichever occurs first. Patients removed from study for unacceptable adverse events will be followed until resolution or stabilization of the adverse event. Follow-up after the conclusion of adjuvant TMZ + DSF will be per routine clinical care. Two years after the patient comes off study, the chart will be reviewed to collect data on progression and survival.

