## 12.0 MEASUREMENT OF EFFECT

### 12.1 Antitumor Effect – Solid Tumors

For the purposes of this study, patients should be re-evaluated for response every 9 +/- 1 weeks. In addition to a baseline scan, confirmatory scans should also be obtained 9 weeks (not less than 4) weeks following initial documentation of objective response.

Response and progression will be evaluated in this study using the updated response assessment criteria for high-grade gliomas: Response Assessment in Neuro-Oncology (RANO) working group guideline [78].

Criteria for Determining First Progression Depending on Time from Initial Chemoradiotherapy

First Progression	Definition
Progressive disease < 12 weeks after completion of chemoradiotherapy	Progression can only be defined using diagnostic imaging if there is new enhancement outside of the radiation field (beyond the high-dose region or 80% isodose line) or if there is unequivocal evidence of viable tumor on histopathologic sampling (eg, solid tumor areas [ie, > 70% tumor cell nuclei in areas], high or progressive increase in MIB-1 proliferation index compared with prior biopsy, or evidence for histologic progression or increased anaplasia in tumor). Note: Given the difficulty of differentiating true progression from pseudoprogression, clinical decline alone, in the absence of radiographic or histologic confirmation of progression, will not be sufficient for definition of progressive disease in the first 12 weeks after completion of concurrent chemoradiotherapy.

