## 14.0 STATISTICAL CONSIDERATIONS

### 14.1 Definition of Primary Endpoint

The maximum tolerated dose (MTD) of DSF with concurrent RT+TMZ will be defined as the dose associated with a 20% probability of dose-limiting toxicity (DLT). Toxicity will be coded using CTCAE version 4.0, and DLT will be defined as toxicity that occurs within 18 weeks from the first day of RT and is possibly, probably or definitely related to DSF/Cu (or 12 weeks from the completion of RT if there is a delay/interruption of RT).

For the expansion cohort of GBM with *IDH*, *BRAF*, and *NF1* mutations, the overall survival (OS) of this molecularly-defined cohort will be measured from the first day of RT.

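### The expansion cohort's OS set excludes and replaces anyone without 4 weeks of DSF with RT, yet OS is timed from RT day 1 against an unconditional 40% benchmark

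*Combined protocol and SAP*

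**What the plan says.** Section 14.3.5 sizes the expansion comparison: 24 patients, 80% power, one-sided alpha 0.10, 2-year OS of 40% (historical) against 60%. Nine of the 24 come from the escalation phase, so "only additional 15 patients will be needed". The section then states that expansion "patients are considered evaluable if a patient has received at least 4 weeks of DSF with RT", at either 375 or 250 mg/day, and "Inevaluable patients will be replaced".

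Sections 2.0 and 14.1 make OS the primary endpoint of this phase: "the overall survival (OS) of this molecularly-defined cohort will be measured from the first day of RT". The 40% benchmark is an average of about 50% (IDH-mutant) and 30% (BRAF/NF1), with no condition on surviving or tolerating the first 4 weeks.

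No section defines an all-treated set for OS, a landmark start, or an analysis that brings replaced patients back. Section 14.4 names Kaplan-Meier without a population. The nearest alternative is the rule in 5.9.3, which serves DLT only: "Patients who do not have at least one dose of DSF with RT+TMZ will not be evaluable for DLT and will be replaced".

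**The concern.** Entry to the analysis depends on something that happens after the OS clock starts. A patient who dies in weeks 1 to 4 cannot complete 4 weeks of DSF, is therefore inevaluable, and is replaced by someone else. This is immortal time, and it can only raise observed OS relative to the benchmark.

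The rule also removes patients who are alive at week 4 but stopped DSF early for toxicity or refusal. Section 6.2 stops DSF/Cu during RT for a DSF-related event that needs a dose reduction, yet allows expansion patients who stopped for toxicity to be considered for DSF again in the adjuvant phase. Such a patient could be back on study drug and still be outside the primary endpoint. Whether these removals bias the result depends on how the patients survive.

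The rule matters mainly for the 15 new patients. The 9 carried-over patients had 100% 1-year OS (section 1.3), so none of them died early.

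**Working it through.** **The plan's own figure.** The test is not named, but N = 24 can be reproduced on the log(-log) survival scale with the null variance. V0 = (1-0.4)/(0.4 × ln²0.4) = 1.787; difference d = ln(-ln 0.4) - ln(-ln 0.6) = 0.584; N = (1.2816+0.8416)² × 1.787/0.584² = 23.6, rounded up to 24. Power at 24 is 80.5%. The sample-size arithmetic is sound. The fault is in who is counted.

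**Inputs.** From 14.3.5: null 2-year OS 40%; strata 50% and 30%; 9 carried over (6 IDH, 3 BRAF/NF1) and 15 new (6 and 9). Assumed: the share f of new patients dropped and their 2-year OS q. The documents give neither.

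**Deaths before day 28.** Constant hazard λ = -ln(0.40)/2 = 0.458 per year. Share f = 1 - exp(-0.458 × 28/365.25) = 0.0345.

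**Null OS of the retained new patients.** p = (0.40 - f·q)/(1 - f). With f = 0.0345 and q = 0, p = 0.40/0.9655 = 0.414.

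**Type I error.** Exact upper tail of Binomial(9, 0.40) + Binomial(15, p). As no cutoff is stated, two are shown:

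| Dropped share f | 2-year OS of dropped, q | ≥13/24 | ≥14/24 |
|---|---|---|---|
| 0 | – | 0.114 | 0.053 |
| 1% | 0 | 0.119 | 0.056 |
| 3.5% | 0 | 0.133 | 0.064 |
| 5% | 0 | 0.142 | 0.070 |
| 10% | 20% | 0.144 | 0.071 |
| 10% | 0 | 0.178 | 0.092 |
| 12.5% | 20% | 0.153 | 0.076 |
| 12.5% | 0 | 0.199 | 0.105 |
| any | 40% | 0.114 | 0.053 |

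Rows with f of 1 to 5% are early deaths only. Rows at 10 to 12.5% add early stoppers.

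**Stratum-specific rates, early deaths only.** The shares are 2.6% (IDH) and 4.5% (BRAF/NF1), so the null rates of new patients become 0.513 and 0.314. Error moves from 0.109 to 0.127 (≥13/24) and from 0.050 to 0.060 (≥14/24).

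**One-sample log-rank.** Reject if (E-O)/√E > 1.2816. By simulation, with the 15 new patients conditioned on surviving 28 days but timed from day 0, error moves from 0.087 to 0.109 with 2 years of follow-up, and from 0.087 to 0.106 with 2.65 years.

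**Expected replacements.** 15/(1-f) - 15 = 0.5 at 3.5% and 2.1 at 12.5%.

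**The case against.** - **The rule may govern accrual only.** It stands under a sample-size heading, and 14.1 defines OS for the molecular cohort with no evaluability condition. But a replaced patient is by definition not one of the 24 in the section that sizes the OS comparison, and no other OS set exists. If the sponsor means something else, the plan has to say so.
- **The 3.5% is assumed and may be high.** This stands. It spreads a 2-year average hazard over the first month, and patients must have KPS of at least 60 and be eligible for the full RT course. Section 12.1 also makes early declared progression rare, since "clinical decline alone, in the absence of radiographic or histologic confirmation of progression, will not be sufficient" within 12 weeks of chemoradiotherapy. The nearest figures, in 1.1, are 5% unable to complete 90% of RT and 13% not completing concurrent TMZ. Neither is a 4-week DSF figure. At 1% the error moves by half a point or less.
- **A cutoff of 13 of 24 already exceeds 0.10 with no exclusions.** This stands. Under 14 of 24, early deaths alone leave the error at 0.064.
- **The carried-over patients are modelled at 40% although all were alive at 1 year.** This is a fair limit on the absolute error rates. Under constant hazard their null 2-year OS would be √0.40 = 63%, and the error at ≥14/24 would be 0.224, rising to 0.253 with early deaths dropped. That is a separate and larger problem. It does not remove this one, and the shift keeps its direction.
- **Early deaths are still reported as safety data.** True, but that does not put them into the primary endpoint.

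**Conclusion.** The concern holds. The evaluability rule and the OS time origin do not match, and the resulting bias from early deaths always favours the regimen. Its certain part is about 1.4 points of 2-year OS for the 15 new patients, against a target gain of 20 points. That adds roughly 1 to 2 points of type I error, depending on the test. This rests on an assumed 3.5% dying before day 28; a share of 1 to 5% gives 0.119 to 0.142 (≥13/24) or 0.056 to 0.070 (≥14/24).

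The larger figures, up to 0.199, need 10 to 12.5% dropped with 2-year OS of at most 20%, which the documents do not support or exclude. If the dropped patients survive at 40%, nothing changes. The point should be fixed because it touches the primary endpoint and costs almost nothing to correct. It does not invalidate the design.

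**What to change.** In 14.3.5, define the primary OS set as every patient with an IDH, BRAF or NF1 mutation who receives at least one dose of DSF with RT/TMZ (the threshold 5.9.3 already applies for DLT), timed from the first day of RT. State that no patient is replaced in the OS analysis because of DSF duration.

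The 4-week set can stay as a secondary analysis of patients alive at a 4-week landmark. OS should then be counted from the landmark and the benchmark conditioned on reaching it. Under constant hazard that benchmark is about 41.4% at the point 2 years after RT start, and 40% at 2 years after the landmark itself.

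The cost is about two sentences. No new data are needed, because 5.13 already provides the follow-up: "Two years after the patient comes off study, the chart will be reviewed to collect data on progression and survival". That reaches 2-year OS for early stoppers too. The downside is a slightly less favourable OS estimate that includes some patients with little DSF exposure.
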